6.1 Study Endpoints

6.1.1 Primary endpoints

- 1) Incidence of ARs within 0–28 days after booster immunization.
- 2) Geometric mean titer (GMT) of anti-SARS-CoV-2 specific neutralizing antibodies against omicron BA.4/5 in subjects in the immunogenicity group at 28 days after booster immunization.

6.1.2 Secondary endpoints

Immunogenicity endpoints:

- 1) Seroconversion rate and geometric mean increase (GMI) of anti-SARS-CoV-2 neutralizing antibodies in subjects in the immunogenicity group at 28 days after immunization;
- 2) Seroconversion rate, GMT, and GMI of anti-SARS-CoV-2 neutralizing antibodies in subjects in the immunogenicity group at 14 days, 3 months, and 6 months after booster immunization;
- 3) Geometric mean concentration (GMC), seroconversion rate, and GMI of anti-SARS-CoV-2 RBD protein IgG antibodies in subjects in the immunogenicity group at 14 days, 28 days, 3 months, and 6 months after booster immunization.

Safety endpoints:

- 1) Incidence of adverse reactions within 30 minutes after booster immunization;
- 2) Incidence of adverse reactions within 0–14 days after booster immunization;
- 3) Incidence of adverse events within 0–28 days after booster immunization;
- 4) Incidence of serious adverse events (SAEs) within 6 months after booster immunization.

Exploratory endpoints:

- 1) Baseline anti-Ad5 vector neutralizing antibody titer in subjects in the immunogenicity group, and stratified analysis based on baseline anti-Ad5 vector neutralizing antibody titer ($> 1:200$, $\leq 1:200$);
- 2) GMT, seroconversion rate, and GMI of certain VOC/VOI cross-neutralizing antibodies in subjects in the immunogenicity group at 28 days after booster immunization;

- 3) GMC, seroconversion rate, and GMI of salivary IgA and serum IgA antibodies in subjects in the immunogenicity group at 14 days, 28 days, 3 months, and 6 months after booster immunization;
- 4) Seropositive rate and response levels of IFN- γ , TNF- α , IL-2, IL-4, IL-5, and IL-13 in CD4⁺ and CD8⁺ stimulated by S protein overlapping peptide library using ICS in subjects in the cellular immunization group at 14 days after booster immunization.

6.2 Sample Size Estimation

This study includes a safety group and an immunogenicity group. The immunogenicity group also includes a cellular immunity group. Approximately 10,000 subjects are planned to be enrolled in the safety group. This sample size provides at least 85% power to detect 1 case of adverse reaction in the investigational vaccine group with an incidence of 0.02% (assuming that the background incidence of a given adverse event is 1 in a million).

Rationale for sample size determination in the immunogenicity group: Based on data from preliminary clinical studies (Project No.: JSVCT127), the GMT of anti-SARS-CoV-2 neutralizing antibodies at 28 days after administering a booster dose of the inactivated vaccine in the control group was around 16. The GMT, standard deviation, of anti-SARS-CoV-2 neutralizing antibodies at 28 days after immunization in the investigational vaccine group were 32, and 9, respectively. Using PASS 15.0 procedure of Two-Sample T-Tests Assuming Equal Variance, 183 subjects in each of the investigational vaccine group and the control group (1:1 ratio) will be required for a one-sided $\alpha = 0.025$ test with at least 85% power to demonstrate that the antibody titer after booster dose in the investigational vaccine group is superior to the control group. Considering the dropout of the study, 420 subjects will be enrolled in the immunogenicity subgroup. The cellular immunity group will consist of the first 60 subjects in the immunogenicity group of a single site managed by Jiangsu CDC.

6.3 Coding Rules

6.3.1 Screening number

After registration at the study site, each subject is given a unique screening number. Each screening number corresponds to only one subject. Rule for screening number at each site: S + site number + 4 digits.

6.3.2 Randomization numbering rules

Before vaccination during V1, each subject is assigned a unique randomization number by the study personnel on site via the IWRS system according to their enrollment sequence. Each randomization number corresponds to only one subject until the end of the study.

This study intends to enroll 10420 subjects aged 18 years and above, of which the population aged 60 years and above accounts for approximately $\geq 30\%$. A total of 6 study centers will be established (each study site may set up multiple vaccination sites). The 420 subjects in the immunogenicity group will be randomized to receive a booster dose of Ad5-nCoV-IH or inactivated SARS-CoV-2 vaccine in a 1:1 ratio. Rule for randomization numbers: Site number + 4-digit serial number, each site number will start with 0001. Jiangsu CDC + 0001–0060 will also be included in the cellular immunity subgroup. In the case of a subject dropping out after randomization but before vaccination, a substitute may be randomized. For example, if subject 0001 drops out before vaccination, the next enrolled subject will be the substitute with a randomization number of 10001; if the substitute also drops out before vaccination, the next enrolled subject will be a substitute with a randomization number of 20001; 9 substitutes is the maximum.

6.4 Study Duration

Expected start time: Jan. 2022.

Expected end time: Jun. 2023.

6.5 Study Interruption and Premature Termination

The investigator collects AEs of subjects after immunization. In the case of violations against the protocol, GCP requirements, or ethical requirements, the PI, IEC, or administrative departments have the right to suspend or terminate the study, and have the obligation to notify other parties and subjects and explain the reasons.

The trial should be suspended, and the investigator should hold an expert panel meeting to decide whether to terminate the clinical trial prematurely if any of the following situations occur:

- One subject of Grade 4 or greater adverse reactions possibly related to vaccination;
- One subject of serious or life-threatening SUSAR;
- The number of subjects with Grade 3 adverse reactions and symptoms lasting more than 48 h without remission to Grade 1 or Grade 2 exceeds 15% of vaccinated subjects.

In case of any of the following circumstances, the study should be terminated:

- The IEC requests a complete termination of trial with reasons;
- The administrative department requests a complete termination of trial with reasons.

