6. STUDY DESIGN

Study design:

Multi-center, open-label clinical study, with a randomized, controlled immunogenicity group.

Randomization:

A total of 420 subjects in the immunogenicity group will be randomized in a 1:1 ratio to receive a booster dose of Ad5-nCoV-IH or ICV. Authorized investigators may assign each enrolled subject a study ID via the IWRS system. The investigators responsible for managing the vaccines will use the investigational vaccine that corresponds to the study ID and group allocation information.

Study design:

This study intends to enroll 10420 subjects aged 18 years and above, of which the population aged 60 years and above accounts for approximately $\geq 30\%$. This study includes a safety group and an immunogenicity group. The immunogenicity group also includes a cellular immunity group.

The immunogenicity group will include 420 subjects, and subjects ≥ 60 years should account for $\geq 30\%$ of the population. Eligible subjects who passed consultation and screening and provided informed consent will be randomized in a 1:1 ratio to receive a booster dose of either ICV or Ad5- nCoV-IH. Except for the Jiangsu CDC, the first 60 subjects from a single site of each of the other 5 centers will be included in the immunogenicity group. The first 120 subjects from a single site of the Jiangsu CDC will be included in the immunogenicity group, and the first 60 of these subjects will be included in the cellular immunity group.

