Subjects assigned to receive an ICV booster dose will receive the vaccine from the same manufacturer as the two-dose prime immunization. All subjects will be issued diary cards on the day of vaccination and on Day 14 after vaccination for systematic safety observations. Venous blood and saliva samples will be collected from subjects in the immunogenicity group on the day of vaccination as well as 14 days, 28 days, 3 months, and 6 months after vaccination to test for serum antibody titers, serum IgA, and SIgA. Venous blood samples will be collected from subjects in the cellular immunity group on the day of vaccination and 14 days after vaccination to test for cellular immunity. All subjects are required to complete interviews on the day of vaccination as well as 14 and 28 days after vaccination. Subjects in the immunogenicity group are also required to complete 3- and 6-month follow-up visits. The remaining subjects may complete the 3- and 6-month visits via telephone follow-up. When about 2000 subjects (first stage) and 5000 subjects (second stage) are enrolled, the safety of all subjects in the early stage should be evaluated, and the enrollment schedule should be continued with the consent of PI. Enrollment will be suspended

or terminated immediately if a safety issue with vaccination is found to meet the suspension or termination criteria.

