8.7 Safety Follow-Up and Evaluation

8.7.1 Safety observation

All subjects will remain on site for a 30-min observation period after receiving the vaccination. Investigators will observe each and every one of the subjects and record both regional and systemic responses reported during the 30-min observation period, as well as their severity.

A safety follow-up will be performed within 14 days after vaccination for all subjects, during which the investigator will systematically examine each subject for ARs, and the subject will fill in the "Vaccination Diary Card (Within 14 Days)" according to their symptoms and signs. From day 15 to day 28 after vaccination, post-vaccination AEs should be observed through spontaneous reporting and regular follow-ups. The investigators will inquire and check the diary cards at the next visit and guide the subjects in completing the cards. From day 28 to month 6 after vaccination, safety follow-ups on SAEs should be performed by spontaneous reporting.

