8.8 Immunogenicity Evaluation

8.8.1 Sample collection

For the immunogenicity group, 10.0 mL of venous blood will be collected on day 0 (V1), day 14 (V2, time window of ± 3 days), day 28 (V3, time window of ± 5 days), month 3 (V4, time window of ± 15 days), and month 6 (V5, time window of ± 15 days) after vaccination, and 2.0 mL of saliva will be collected on day 0 (V1), day 14 (V2), day 28 (V3, time window of ± 5 days), month 3 (V4, time window of ± 15 days), and month 6 (V5, time window of ± 15 days) after vaccination. For subjects in the cellular immunity group, 15.0 mL of venous blood will be collected on day 0 (V1) and day 14 (V2, time window of ± 3 days) after vaccination.

Vacuum blood collection tubes containing serum separator gels are used. Sample refrigeration prior to centrifugation is not allowed in order to minimize the risk of hemolysis and to avoid blood cell contamination during serum transfer to the target serum tube. Serum is separated on the blood collection day and stored at $-20\text{ }^{\circ}\text{C}$ or below for serum antibody testing and backup.

According to the operating manual, the saliva samples will be stored at -20°C or below and delivered to the testing laboratory in time.

Cellular immunity samples will be collected in vacuum blood collection tubes with anticoagulant. PBMC will be separated and used for ICS on the day of blood collection.

The serum and saliva samples collected in this clinical trial will be used to evaluate the immune response of the investigational vaccine. Approval by the Institutional Review Board and consent of the subjects are required if used for other research purposes. Except for serum and saliva samples that are sent for testing, remaining backup samples will be transferred to a third-party laboratory at the end of the clinical trial. Blood and saliva samples may not be delivered abroad.

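### The 15% suspension rule counts subjects vaccinated too recently to have a qualifying reaction, so the observed proportion runs below the true rate during enrolment and the rule can fire late

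*Protocol*

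**What the plan says.** Section 6.5, repeated in the synopsis, lists three suspension triggers. Two are met by a single subject: a Grade 4 or greater reaction possibly related to vaccination, or a serious or life-threatening SUSAR. The third is a proportion. It is met when the number of subjects with Grade 3 reactions and "symptoms lasting more than 48 h without remission to Grade 1 or Grade 2 exceeds 15% of vaccinated subjects". No minimum follow-up or evaluable subset is attached.

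On data capture, section 8.7.1 provides 30 minutes of on-site observation, then a 14-day diary card. It adds: "The investigators will inquire and check the diary cards at the next visit". The 0-14 day card is returned at V2, whose timing section 8.8.1 gives as "day 14 (V2, time window of ± 3 days". Section 8.7.1 also has the investigator examine subjects for reactions within the 14 days, and section 8.7.5 asks subjects to report clinically significant events promptly.

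On enrolment, section 6 states: "This study intends to enroll 10420 subjects aged 18 years and above". Safety is evaluated "When about 2000 subjects (first stage) and 5000 subjects (second stage) are enrolled", after which "the enrollment schedule should be continued with the consent of PI". These reviews are triggered by a head count and carry no follow-up requirement. Section 6 also ties suspension of enrolment to the same criteria.

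**The concern.** A subject enters the numerator only after a Grade 3 reaction has lasted more than 48 h, but enters the denominator on the day of vaccination. Recent recipients are in effect counted as free of an event that they have not had time to show. The effective threshold is then not 15%. It is higher, it depends on how fast subjects are being vaccinated, and it is furthest from 15% early in enrolment, when most subjects are still to be exposed.

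The rule exists to limit exposure if reactions prove unexpectedly frequent, so the harm is lateness. The single-subject triggers do not close the gap. Table 8.7-1 defines no Grade 4 for any of the five local reactions to the inhaled vaccine. For those, unless one qualifies as a SUSAR, the proportion is the only listed trigger.

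**Working it through.** **Plan's figure.** The 15% is stated without derivation, so there is nothing to reproduce. In counts, exceeding 15% means 301 of 2000, 751 of 5000 or 1564 of 10420.

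**Inputs from the protocol.** The threshold, the denominator, the 48 h condition, the 10420 planned, the reviews at 2000 and 5000, and V2 at day 14 ± 3. Section 11 gives a total duration of about 15 months. Less 6 months of follow-up, this leaves at most about 9 months (270 days) for enrolment. The dates in section 6.4 allow somewhat longer, which would only shrink the effect.

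**Assumptions.** Uniform enrolment over T days (or at a stated daily pace), and a single lag L from vaccination to a countable event. L cannot be below just over 2 days. L = 14 represents capture only at the diary check and is a worst case.

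**Formulas.** With n vaccinated, t = T × n / 10420 (or n / pace). The evaluable share is e = max(0, (t − L)/t). The observed proportion is p × e, so the true rate needed is 15%/e. If e is 15% or less, the rule cannot fire at that moment.

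**True rate needed at 2000 vaccinated:**

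| Enrolment | t (days) | L = 2 | L = 3 | L = 14 |
|---|---|---|---|---|
| T = 270 days | 51.8 | 15.6% | 15.9% | 20.6% |
| T = 90 days | 17.3 | 17.0% | 18.2% | 79% |
| 300 per day | 6.7 | 21.4% | 27% | cannot fire yet |
| T = 30 days | 5.8 | 23.0% | 31% | cannot fire yet |

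For example, at 300 per day and L = 3: e = (6.67 − 3)/6.67 = 0.55, and 15%/0.55 = 27%.

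At 5000 vaccinated and T = 270 days, the needed rate falls to 15.4% (L = 3) or 16.8% (L = 14).

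**Chance of exceeding 300 cases at the 2000-subject review, true rate 20% (binomial tail):**

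| Situation | L = 3 | L = 14 |
|---|---|---|
| T = 30 days | 0% | 0% |
| T = 90 days | 97% | 0% |
| T = 270 days | about 100% | 29% |

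If all 2000 were evaluable, the chance would be above 99.9%.

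**Delay.** While enrolment runs, a true rate p above 15% crosses the line at t = pL/(p − 0.15). At p = 20% this is 0.20 × 3/0.05 = day 12 for L = 3, and 0.20 × 14/0.05 = day 56 for L = 14. Subjects vaccinated by then, t/T × 10420:
- T = 270 days: about 460 (L = 3) or 2160 (L = 14).
- T = 90 days: about 1390 or 6480.
- T = 30 days: about 4170 for L = 3. For L = 14, enrolment is complete before the rule fires.

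**The case against.** **The size is assumed.** This stands. No pace is stated. With nine-month enrolment and prompt detection, the effective threshold is about 16% rather than 15%, which is negligible. A reader might infer that the bias is always substantial, but the protocol does not support that. Even at 100 per day (t = 20 days at 2000 vaccinated), L = 2 gives a shortfall of only 2/20 = 10%.

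**A 14-day lag is a worst case.** This also stands. Section 8.7.1 provides for examination within the 14 days and section 8.7.5 for prompt self-report. A Grade 3 local reaction to inhalation is by definition one that needs treatment, so many would be known before V2. The results at L = 14 bound the effect and do not predict it. Self-report cannot, however, bring the lag below 48 h.

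**A reader might infer that the rule cannot work at all.** The documents do not support this. Being unable to fire requires more than about 85% of those vaccinated to lie inside the lag, which needs very fast enrolment or a long lag, and it is temporary. A sustained rate above 15% does eventually cross the line.

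**Nor is this the only numeric safety limit.** The Grade 4 and SUSAR triggers are set at one subject, have no denominator and are not diluted. The 15% rule is the only rate-based limit.

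**It is unlikely to matter in practice.** Section 3.4.2 reports Grade 3 reactions of any duration in 2 (1.43%) of each inhaled group. At such a rate neither denominator triggers. That is true, but a suspension rule is written for the unexpected case and should then act at its stated threshold.

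**The staged reviews may catch a problem.** They evaluate safety more widely than this one proportion, but they require no follow-up, so they do not repair it.

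**Conclusion.** The point holds as to direction. From the wording alone, for any lag above zero, the observed proportion is below the true rate while enrolment runs and the rule can fire late. The size rests on an assumed pace and lag. At the 2000-subject review the true rate needed is about 16% for enrolment over nine months with a short lag, about 27-31% for 300 per day or 30-day enrolment with a 3-day lag, and temporarily out of reach for fast enrolment with a 14-day lag. The consequence is confined to true rates above 15% but below the diluted threshold. This is a defect in how the rule is defined, worth a short correction. It does not show that the trial lacks safety limits, and no view is taken on whether 15% is the right figure.

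**What to change.** Leave the 15% figure and the action unchanged. In section 6.5 and in the synopsis, define both numerator and denominator in the same cohort: vaccinated subjects whose safety information covers one fixed interval after vaccination. The sponsor should set the interval and state it in both places. Beside the proportion, report the number vaccinated but not yet evaluable and any qualifying reactions already known among them.

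Do not add early cases to a denominator of completed subjects. Cases would then enter at once and non-cases only after the interval, which biases the proportion upward. For example, take 300 per day, a 14-day interval, cases known at day 3 and a rate of 1.43%. On day 15 there would be 0.0143 × 300 × 12 = 51 cases against 0.9857 × 300 × 1 = 296 completed non-cases, which reads 51/347 = 15%. Before that day, by which some 4500 subjects are vaccinated, it would read above 15% although the true rate is 1.43%.

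The cost is one sentence in two places and a count from the EDC system. The proportion rests on fewer subjects early on and is noisier, and known early cases enter it slightly later, although they are shown alongside.

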7 STUDY POPULATION

7.1 Selection of Study Population

Subjects aged 18 years and above who have received two doses of inactivated SARS-CoV-2 vaccine ≥ 6 months from the booster immunization will be selected on the principle of informed consent from volunteers and voluntary participation. Among them, subjects ≥ 60 years should account for $\geq 30\%$ of the population.

7.2 Inclusion Criteria

- 1) Volunteers aged 18 years and above at the time of screening;
- 2) Volunteers who provided informed consent and signed the informed consent form;
- 3) Volunteers who are able and willing to comply with the requirements of the clinical trial protocol, and can complete the 6-month follow-up;
- 4) Completed 2 doses of vaccination with inactivated SARS-CoV-2 vaccine ≥ 6 months prior to the planned vaccination in this study.

7.3 Exclusion Criteria

- 1) Subjects with a history or family history of convulsions, epilepsy, encephalopathy, or mental disorders;
- 2) Subjects who are allergic to any ingredient of the investigational vaccine, or subjects with a history of severe anaphylactic reactions to vaccines, allergies, or asthma;
- 3) Those with a history of severe vaccine-related ARs following immunization with a vaccine;
- 4) Females who tested positive for urine pregnancy test;
- 5) Subjects with acute febrile disorders, infectious disease, or a history of SARS;
- 6) Axillary temperature > 37.0 °C;
- 7) Subjects with serious cardiovascular diseases, such as arrhythmia, heart block, myocardial infarction, and serious, uncontrolled hypertension despite antihypertensive drugs (on-site measurement: SBP ≥ 180 mmHg and DBP ≥ 110 mmHg);
- 8) Subjects with serious chronic diseases or progressive diseases that cannot be controlled, such as diabetes or thyroid disorders;
- 9) Subjects with congenital or acquired angioedema/neurogenic edema;
- 10) Subjects with a history of urticaria within 1 year prior to receiving the investigational vaccine;

- 11) Subjects with asplenia or functional asplenia;
- 12) Subjects with lung function abnormalities such as chronic obstructive pulmonary disease or pulmonary fibrosis;
- 13) Subjects with a history of COVID-19 infection/disease;
- 14) Subjects with epidemiological exposure to SARS-CoV-2, or travel history to areas of moderate/high risk or abroad within the past 21 days;
- 15) Those who are judged by the investigator with any contradiction to the study protocol or the signing of informed consent being affected due to various medical, psychological, social, or other conditions.

